7.5.2 Concomitant Medications

The number and percentage of patients receiving concomitant medications or treatments prior to and during each study stage and over both study stages will be tabulated and presented overall and by treatment group for the Safety analysis population. Concomitant medications and treatments will be summarized using descriptive statistics and will be presented by type of drug (WHO DRUG classification preferred term and Anatomical Therapeutic Chemical Classification [ATC] level 1) by treatment group.

7.5.3 Clinical Laboratory Tests

Summary of observed values and changes from baseline (last measurement prior to entering the study) will be summarized at each visit. In addition, for laboratory adverse events, severity will be graded by CTCAE, when such grading is available. The frequency of subjects with values below, within, and above the normal reference range will be also be summarized in shift tables at each visit. Worst CTCAE grade will be presented for Stage 1, Stage 2, Week 144 – end of the study, and over the entire study. A subject having the same abnormality more than once within a time interval will be counted only once based on the worst severity grade observed.

7.5.4 Vital Signs

Vital signs will be listed for each subject. These will include temperature, respiration, pulse, and blood pressure. Summaries over time and changes from baseline will be provided at each visit.

7.5.5 Physical Examinations and Other Parameters

Height, weight, physical examination, ophthalmoscopy, slit-lamp examination, and visual fields will be summarized by visit using descriptive statistics over the course of the study. Medications taken prior to entering the study and started while on study (i.e., concomitant) will be summarized to Week 48, from Week 48 to Week 148, and through end of treatment, including sub-study.

7.6

[REDACTED]

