## 11 STATISTICS

### 11.1 Sample Size

The study is planned to enroll a minimum of 36 subjects with nonsense mutation aniridia who are  $\geq 2$  years of age. This number of subjects should provide adequate information to evaluate the safety of ataluren in this population. For a statistical hypothesis test for any efficacy endpoint, the study will have 60% power to detect an effect size (i.e., standardized mean difference) of 0.85, or 80% power to detect an effect size of 1.06, at the 0.05 significance level (two-sided).

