### 11.8.3 Other Parameters

Height, weight, vital signs, physical examination, ophthalmoscopy, slit-lamp examination, and visual fields will be summarized descriptively.

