#### **13.1.2 Reproductive Considerations**

Ataluren is not genotoxic, did not affect fertility in male and female rats, and was not teratogenic in rats and rabbits. In addition, lack of sexual maturity in many of the subjects likely to be enrolled in this study limits reproductive risks. However, restriction on eligibility relating to willingness to avoid unprotected sexual intercourse in any subjects known to be sexually active is included as a general precaution. Because it is unknown if ataluren is excreted in breast milk, lactating female subjects who are breast-feeding are excluded from participation.

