### 13.2.3.9 *Body Mass Index*

Systemic abnormalities associated with aniridia include increased body mass index (BMI) and obesity ([Netland 2011](#)). Accordingly, BMI will be calculated.

[REDACTED]

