2.5 Sample Size

The study was planned to enroll a minimum of 36 subjects with nonsense mutation aniridia who are ≥ 2 years of age. This number of subjects has been reduced to 24 and should provide adequate information for an initial evaluation the efficacy safety of ataluren in this population.

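### Height and weight have no age- and sex-standardised summary, so open-label changes cannot be separated from normal growth

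*SAP*

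**What the plan says.** SAP 7.5.5 covers height and weight in one sentence: "Height, weight, physical examination, ophthalmoscopy, slit-lamp examination, and visual fields will be summarized by visit using descriptive statistics over the course of the study". Protocol 11.8.3 is to the same effect: "Height, weight, vital signs, physical examination, ophthalmoscopy, slit-lamp examination, and visual fields will be summarized descriptively". SAP 7.5.5 does not itself mention change from baseline. That can only be inferred from SAP 7.2, which treats visit-specific safety data like efficacy data but without hypothesis tests.

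On BMI, Protocol 13.2.3.9 says "Accordingly, BMI will be calculated". In the visible SAP it appears only among the baseline characteristics (7.3.2).

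Subjects are eligible from age 2 with no upper limit (Protocol 4.2). Protocol 13.1.2 refers to "lack of sexual maturity in many of the subjects likely to be enrolled in this study", while the contraception criteria in Protocol 4.2 also provide for postmenopausal women. Children and adults therefore share the same tables. Randomisation is 2:1, stratified at age 10. Placebo ends at Week 48. Open-label ataluren follows to Week 144, then to Week 240 for those who choose the sub-study (Protocol 1.2).

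For laboratory values, SAP 7.5.3 plans "Summary of observed values and changes from baseline (last measurement prior to entering the study) will be summarized at each visit". The same paragraph adds shift tables against the reference range and worst CTCAE grades.

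**The concern.** Children grow whatever they are given, and adults do not. A by-visit mean of raw height or weight in a mixed cohort therefore depends largely on how old the subjects at that visit are. Systemic safety of long-term ataluren is a secondary objective. The protocol ties aniridia to overweight and obesity (2.1) and gives BMI a place in its outcome rationale (13.2.3.9). If the drug slowed growth or added weight, the open-label tables as planned could not show it, nor could they give positive reassurance that it did not. SAP 7.7 puts age or age stratum into every secondary efficacy model, but the visible plan has no counterpart for the two measurements that depend most on age.

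**Working it through.** **1. The plan's own figure.** The only power statement is for efficacy. Protocol 11.1 ("The study is planned to enroll a minimum of 36 subjects with nonsense mutation aniridia who are" at least 2 years old) says "the study will have 60% power to detect an effect size (i.e., standardized mean difference) of 0.85", or 80% for 1.06. A two-sample t-test at 24:12, two-sided 0.05, gives 64.7% and 83.0%. The stated pairs are matched at 22:11 (60.6% and 79.4%). Nothing is stated for growth, and nothing below depends on these figures. They matter only for the sample size: SAP 2.5 says "This number of subjects has been reduced to 24", while SAP 7.1 keeps 36, so I show both 24:12 and 16:8.

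**2. Size of normal growth (assumed rates).** 48 weeks = 48 × 7 / 365.25 = 0.92 years; the open-label stage, Week 48 to 144, = 1.84 years; 240 weeks = 4.60 years. Assume a growing child gains 5 to 7 cm and 2 to 3.5 kg a year, and an adult gains nothing.

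- By Week 48: 0.92 × 5 to 0.92 × 7 = 4.6 to 6.4 cm; 1.8 to 3.2 kg.
- Week 48 to 144: 1.84 × 5 to 1.84 × 7 = 9.2 to 12.9 cm.
- By Week 240: 4.60 × 5 to 4.60 × 7 = 23 to 32 cm; 9 to 16 kg.

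**3. Chance imbalance to Week 48.** In a placebo arm of 8, one child is 12.5 percentage points. If the share of growing subjects differs by 10 to 20 points between arms, growth alone separates the mean weight changes by 0.10 × 1.84 = 0.18 kg to 0.20 × 3.22 = 0.64 kg. The stratification limits this, but the stratum over 10 still mixes adolescents with adults.

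**4. Noise to Week 48.** I simulated 48-week height change, 4,000 trials per cell. All inputs are assumptions: expected velocity 9 cm/year at age 2, mostly 5.5 to 7 from age 4 to mid-puberty, then falling to 0 at 18; SD of individual velocity 0.8 cm/year; measurement SD 0.4 cm; ages uniform from 2 to 18, 40 or 60; any drug slowing acts only under age 17. The raw change was compared with the change net of age-expected growth.

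With no drug effect (24:12), the SD of the change, raw versus net, was 2.12 vs 0.81 cm (ages 2–18), 2.79 vs 0.61 (2–40) and 2.44 vs 0.54 (2–60). Expected growth thus makes up 1 − (0.81/2.12)² = 85% of the raw variance in the first case and about 95% in the other two. The raw comparison rejected in 4 to 5% of null trials, as it should.

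Chance of p<0.05, raw / net:

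| Ages | 24:12, 1 cm/yr | 24:12, 2 cm/yr | 16:8, 1 cm/yr | 16:8, 2 cm/yr |
|---|---|---|---|---|
| 2–18 | 23% / 81% | 66% / 100% | 17% / 62% | 49% / 99% |
| 2–40 | 8% / 26% | 16% / 56% | 7% / 17% | 12% / 33% |
| 2–60 | 6% / 14% | 10% / 27% | 6% / 9% | 9% / 14% |

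No such test is planned, so read these as a measure of sensitivity. The net column is a best case, because it removes exactly the growth that was put in. The simulation did not stratify at age 10, which would remove some of the raw noise.

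**5. After Week 48.** On the same inputs, the mean height gain over 240 weeks with no drug effect is 20.5 cm (ages 2–18), 8.7 cm (2–40) or 5.7 cm (2–60), with SD 11 to 12 cm. A slowing of 1 cm a year takes at most 4.60 × 1 = 4.6 cm off that mean. Moving the upper age from 18 to 40 moves it by 20.5 − 8.7 = 11.8 cm. With no concurrent control and no reference, a raw mean cannot tell the two apart. The age mix can also shift between visits as subjects leave or decline the sub-study.

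**The case against.** The best defence starts with the design. To Week 48 there is a randomised placebo arm stratified by age, so growth is balanced in expectation and the null rejection rates above bear that out. Height and weight are not listed in the secondary safety endpoint (Protocol 3.2.2, SAP 3.2), no visible section names growth as an ataluren risk, and the tables are descriptive. Age subgroups are foreseen too: they will be produced under Protocol 11.12 and may be under SAP 7.10. All of this stands, and it keeps the point modest. The subgroups help only in part. The one age split the documents define is at 10 years, which leaves growing adolescents and adults together, and no subgroup restores a control after Week 48.

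A reader might be tempted to go further in three ways.

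- **That growth swamps any drug effect.** No document figure gives the size of growth or of a drug effect. On my assumptions raw data still detect a 2 cm/year slowing 66% of the time in one setting.
- **That kidney safety is judged on raw creatinine alone.** SAP 7.5.3 also plans shift tables and CTCAE grades, and cystatin C is in the biochemistry panel (Protocol 8.3.8), so it gets the same tables. What remains open is narrower: those tables do not adjust for body size, and the documents do not say whether the local laboratories' reference ranges are age-specific.
- **That BMI is never analysed over time.** Objectives, endpoints and analyses are partly redacted (for example SAP 2.3, 3.3, 7.6 and 7.9), and a redaction follows Protocol 13.2.3.9 directly. The absence is from the visible text only.

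**Conclusion.** The point holds for height and weight. Before Week 48 the cost is precision, not validity. After Week 48 the raw summaries confound ataluren exposure with normal growth, to Week 144 for everyone who continues and to Week 240 only for sub-study participants. The size depends on the age mix, which the documents do not give, and every growth figure here is an assumption. For BMI the point is conditional on the redacted text. The renal part is secondary: that creatinine depends on body size is an assumption, and I did not model it. Nothing here touches the primary endpoint. Standardising also has a limit. It removes the growth expected in a reference population, so a drift in z-score after Week 48 could still reflect aniridia itself and would need cautious reading.

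**What to change.** In SAP 7.5.5 and Protocol 11.8.3, for subjects under 20 years at the visit, summarise height and weight as age- and sex-specific z-scores, with change from baseline. Treat BMI the same way unless a redacted section already does. Name the reference in the SAP, and use age at the visit, since SAP 5 defines age only at randomisation. Show adults separately in raw units. Present by arm to Week 48, then for combined ataluren with the Week 48 baseline that SAP 7.2 already sets for the placebo group, continuing to Week 240 for the sub-study.

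An optional addition to SAP 7.5.3 is an age-appropriate eGFR by visit beside the planned creatinine and cystatin C tables, with a statement on whether the local reference ranges are age-specific.

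The cost is a few derived variables, some extra tables and a few lines of text. Date of birth, sex, height, weight, creatinine and cystatin C are already collected.

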7.7 Efficacy Analysis

All efficacy analyses will be conducted in both ITT population as the primary analysis. Visual acuity, corneal keratopathy, and iris area will also be analyzed using the efficacy analysis population as a supportive analysis.

The primary efficacy analysis will be by analysis of covariance (ANCOVA) where baseline Maximum Reading Speed (OU) and age will be included as covariates, with treatment as a fixed effect. LS means for the two treatment arms will be provided along with 95% confidence intervals.

To assess treatment effect on the change from baseline in secondary endpoints, general linear models/ANCOVA models, with baseline adjustment and treatment as factors will be used. For the analysis of MNREAD endpoints, age will be included as a continuous covariate; all other secondary endpoints will include age stratum as a factor in the model.

To adjust for other potential effects, some other appropriate statistical models, e.g., ANCOVA models, and/or mixed effect models, may be explored. The p-value of testing treatment difference will be provided. The trend of assessments overtime may be assessed. A summary of the efficacy endpoints listed above will also be provided by visit to assess the trend. Tests of trend, if performed, would include repeated measures over visits with an appropriate covariance structure fitted (first order autoregressive). The effect of linear time would be fit along with its product with treatment to test for differences in trend over time between the two treatment arms. If missing Week 48 assessments for the primary efficacy endpoint exist, sensitivity analyses will be conducted. The reasons of missing will be reported. Analysis results for data with and without imputations (using methods defined in Section 10.1) will be compared.

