#### 8.1.1.1 Stage 1: Visit 1 (Screening, 4 Weeks Prior to Baseline Visit 2)

The Screening Visit (Visit 1) will occur 4 weeks prior to Baseline Visit 2. Screening procedures will proceed as follows:

- Obtain written informed consent/assent
- Determine if the subject meets the preliminary eligibility criteria:
  - Documentation of the presence of a nonsense mutation in 1 allele of the PAX6 gene as determined by genotyping performed at a laboratory certified by the CAP, or under the CLIA, or by an equivalent organization. *Note: Sponsor review of genotyping documentation is required prior to randomization.*
  - Collect demographic information
  - Collect current and relevant medical history and ophthalmic history
  - Identify concomitant medications used
  - BCVA and refraction

If the subject meets the preliminary eligibility criteria, the following assessments will be performed:

- Ophthalmoscopy
- Vital signs (including systolic and diastolic blood pressure, radial pulse rate, and body temperature): performed after the subject has been in a sitting position for 3 - 5 minutes
- Physical examination
- Height (in centimeters) and weight (in kilograms) will be measured at each clinic visit
- Blood draw for clinical laboratory evaluations:
  - Serum  $\beta$ -HCG, as applicable (sample taken only for female subjects of childbearing potential)
  - Hematology and biochemistry

- Serum viral screen
- Urinalysis
- Schedule Visit 2

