3.2 Secondary Endpoints

The key secondary efficacy endpoints of this study are:

- Change from baseline (Visit 2/Day 1) to Week 48 in Reading Accessibility Index of OU
- Change from baseline (Visit 2/Day 1) to Week 48 in BCVA

Other secondary efficacy endpoints of this study are as follows:

- Percent change from baseline (Visit 2/Day 1) to Week 48 in Maximum Reading Speed of OD and OS
- Change from baseline (Visit 2/Day 1) to Week 48 in Reading Accessibility Index of OD and OS
- Change from baseline (Visit 2/Day 1) to Week 48 in Critical Print Size of OU, OD and OS
- Change from baseline (Visit 2/Day 1) to Week 48 in Reading Acuity of OU, OD and OS
- Change from baseline (Visit 2/Day 1) to Week 48 in severity of corneal keratopathy
- Change from baseline (Visit 2/Day 1) to Week 48 in iris area
- Change from baseline (Visit 2/Day 1, Stage 1) to Week 240 (Sub-study End of Treatment Visit) in BCVA. Note: This endpoint will be assessed only for the cohort of subjects who enroll into the sub-study.

The secondary safety endpoint of this study is the overall systemic and ocular safety profile of ataluren as determined by:

- Incidences of treatment-emergent adverse events (TEAEs)
- Abnormal findings on laboratory assessments
- Vital signs
- Physical examinations
- Ophthalmoscopy
- Slit-lamp examination
- Visual field testing

3.3

[REDACTED]

[REDACTED]

[REDACTED]

[REDACTED]

[REDACTED]

[REDACTED]

[REDACTED]

[REDACTED]

[REDACTED]

[REDACTED]

[REDACTED]

[REDACTED]

[REDACTED]

[REDACTED]

[REDACTED]

[REDACTED]

[REDACTED]

[REDACTED]

[REDACTED]

[REDACTED]

[REDACTED]

[REDACTED]

[REDACTED]

[REDACTED]

[REDACTED]

[REDACTED]

[REDACTED]

[REDACTED]

[REDACTED]

[REDACTED]

[REDACTED]

[REDACTED]

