5 DEFINITIONS

Adverse Event

An adverse event (AE) is any untoward medical occurrence associated with the use of a drug (investigational medicinal product) in humans, whether or not it is considered related to the drug. An adverse event can therefore be any unfavorable and unintended sign (including an abnormal laboratory finding), symptom, or disease in a study subject who is administered study drug in this study. A specific list of occurrences that should be reported as AEs is provided in section 9.1.1 of the study protocol. Subjects must be followed for adverse events for at least 28 days after the last dose of ataluren administration, or until any drug-related adverse events and/or ongoing serious adverse events (SAEs) have resolved or become stable, whichever is later. Any event that starts within 35 days (to account for visit window) after last dose of ataluren will be summarized.

Adverse events will be graded for severity using Common Terminology Criteria for Adverse Events (CTCAE) Version 4 grading, where 1=Mild, 2=Moderate, 3=Severe, 4=Life-threatening, and 5=Fatal.

Relationship to study treatment will be coded using the following categories: Unrelated, Unlikely related, Possibly related, and Probably related. In summaries where relatedness is dichotomized to related or not, Unrelated and Unlikely related will be classified as not related and Possibly related and Probably related will be classified as related.

Serious Adverse Event:

A serious adverse event is defined as an adverse event that

- Results in death
- Is life-threatening (patient is at immediate risk of death from the event as it occurred)
- Requires in-patient hospitalization (formal admission to a hospital for medical reasons) or prolongation of existing hospitalization
- Results in persistent or significant disability/incapacity
- Results in a congenital anomaly/birth defect

Treatment-Emergent AE:

A TEAE is any AE that begins or increases in severity after the initial dose of study drug and within 5 weeks of the last dose of study drug.

Age

Subject's age is defined as from date of birth to randomization date. The formula used is (randomization date – date of birth+1) / 365.25.

Ataluren Exposure

The duration of exposure to ataluren treatment is defined as the last dose date minus the first dose date + 1 day.

Baseline

For any variable, unless otherwise defined, baseline is the last assessment taken prior to the first study drug administration.

Change from Baseline

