10 MISSING DATA HANDLING

10.1 Handling Missing Efficacy Data

Missing data for the primary efficacy endpoint will be imputed through Week 48 using last observation carried forward (LOCF) as the primary method of imputation for the efficacy and ITT analysis populations.

As a sensitivity analysis to the use of LOCF, multiple imputation (using SAS PROC MI and SAS PROC MIANALYZE) will also be used to impute missing endpoint data. Missing data at week 48 will be imputed for the primary endpoint for the ITT population only. Missing data predictors will be baseline MRS, MNREAD baseline parameters of reading acuity index, critical print size, reading acuity, and subject age. Twenty iterations will be generated with a prespecified seed number of 20191015 using the Markov Chain Monte Carlo (MCMC) method.

A second sensitivity analysis will be performed using a tipping point approach. The best and worst MRS change will be selected over the entire sample. These values will be rounded to one decimal places. All ataluren-treated subjects with missing endpoint data will be imputed with the worst value and all placebo treated subjects with missing endpoint data will be imputed with the best value and a p-value derived. Next, all ataluren-treated missing values will be replaced by the next worst value all placebo-treated missing data will be replaced by the next best value and a p-value derived. This process will be continued until all ataluren-treated missing data are replaced with the best value and all placebo-treated missing data are replaced by the worst value. The point at which the p-value “tips” from non-significance to significance will be noted relative to its order and number of analyses performed. In the event that all permutations are statistically significant, then it can be concluded that imputation does not result in a false positive.

Efficacy data will not be imputed for the open-label study period.

If any needed/permitted surgical treatment is performed during the study, and as a consequence, any assessment outcomes are affected significantly due to the surgical procedure, these assessment outcomes on and after the surgery will be set as missing and the last assessment prior to the surgery will be used for later assessment time points.

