Appendix A Schedule of Events

The types and timing of data to be recorded are summarized in Table 1 (Stage 1, double-masked period), Table 2 (Stage 2, open-label period), and Table 3 (open-label sub-study).

Table 1. Schedule of Events (Stage 1)

Protocol Activities		Screening				Double-Masked Treatment			
Day±Window	Week	-28	-4	1 ^a	1	169±28	24	337±28	48/ End of Stage 1 ^b
Visit		1		2		3			4
Informed consent		X							
Medical and ophthalmic history ^c		X							
Serum viral screen		X							
Physical exam		X		X					X
Height and weight		X		X		X			X
Vital signs		X		X		X			X
Ophthalmoscopy		X		X		X			X
Hematology, biochemistry, urinalysis		X				X			X
Serum β-HCG ^d		X		X		X			X
Study drug and diary dispensing				X		X			X
Study drug administration				X		X			X
Study drug compliance and return						X			X
Collect diary						X			X
Adverse events				X		X			X
Concomitant meds		X		X		X			X
MNREAD				X					X
████████████████████				X		X			X
Slit-lamp examination ^e				X		X			X
Slit-lamp photography				X		X			X
OCT				X		X			X
Fundus photography				X		X			X
Humphrey visual fields				X					X
BCVA (visual acuity and refraction) ^f		X		X		X			X
████████████████████				X		X			X
████████████████████				X		X			X
████████████████████ blood				X		X			X
sample for plasma PK ^g									If feasible (i.e., during surgery for glaucoma, cataracts, etc.)

Abbreviations: β -HCG, beta-human chorionic gonadotropin; BCVA, best corrected visual acuity; ETDRS, Early Treatment Diabetic Retinopathy Study; [REDACTED]; LEA, LEA Symbols Visual Acuity Test System; MNREAD, Minnesota Low Vision Reading (MNREAD) Acuity Charts; OCT, optical coherence tomography; PK, pharmacokinetic(s)

^a All study and laboratory assessments on the first day of treatment must be done prior to in-clinic administration of the first dose.

^b Open-label study drug administration will start at the end of Stage 1 (Visit 4/Week 48).

^c Should include capture of available historical values for ocular assessments included in this study, such as visual acuity, [REDACTED], etc.

^d Sample taken only for female subjects of childbearing potential.

^e Slit-lamp examination should precede [REDACTED] measurement.

^f Visual acuity and refraction will be assessed using the Early Treatment Diabetic Retinopathy Study (ETDRS) or an age-appropriate alternative (e.g., LEA).

Table 2. Schedule of Events (Stage 2)

Protocol Activities		Open-Label Treatment						End of Study)/ Early Termination ^a		Follow-Up ^b	

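### The ANCOVA for BCVA, a key secondary endpoint, is valid but leaves the scheduled Screening BCVA unused; adding it as a covariate could gain some precision at little cost

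*SAP*

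**What the plan says.** The key secondary endpoint is "Change from baseline (Visit 2/Day 1) to Week 48 in BCVA" (SAP 3.2). SAP 5 states that "baseline is the last assessment taken prior to the first study drug administration", which for BCVA is the Day 1 value. SAP 7.7 gives the secondary model: "general linear models/ANCOVA models, with baseline adjustment and treatment as factors will be used". It then separates the MNREAD endpoints, which take age as a continuous covariate, from the rest: "all other secondary endpoints will include age stratum as a factor in the model". The BCVA model therefore contains treatment, Day 1 BCVA and age stratum. Beyond that, "some other appropriate statistical models, e.g., ANCOVA models, and/or mixed effect models, may be explored", which commits to nothing.

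BCVA is measured twice before dosing. Protocol 8.1.1.1 lists "BCVA and refraction" at Visit 1, and Protocol 8.1.1.2 lists it again at Visit 2. The Stage 1 schedule in SAP Appendix A (row "BCVA (visual acuity and refraction) ^f") marks Screening, Day 1, Week 24 and Week 48. Protocol 8.3.21 keeps each subject on one chart throughout, so the two pre-dose values share a scale.

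SAP 7.8 tests BCVA third, after Maximum Reading Speed and Reading Accessibility Index. SAP 2.5 reduces the sample size to 24, while SAP 7.1 still gives 36.

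**The concern.** A single acuity reading carries measurement error. If Day 1 BCVA is a noisy measure of a subject's underlying acuity, a second reading four weeks earlier holds information about the Week 48 value that Day 1 alone does not. Both readings precede randomised treatment, so adjusting for both adds no bias. BCVA is one of three tests in the confirmatory sequence of a trial now planned at 24 subjects (16:8 if 2:1 holds). The Screening value should be nearly complete, because it also serves the acuity exclusion. What is at stake is the width of the BCVA confidence interval and the power of the third test, not the test's validity.

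**Working it through.** **The plan's own figure.** SAP 7.1 gives no figure specific to BCVA. It claims, for any efficacy endpoint, 60% power at a standardised difference of 0.85 and 80% at 1.06, with 36 subjects. A two-sided t-test at 24:12 gives 64.7% and 83.0%. The stated pair appears at about 22:11 (60.6% and 79.4%), but no loss of three subjects is stated. At 16:8 the t-test gives 46.7% and 64.8%. The conflict between 36 and 24 is a separate matter; I work at 16:8.

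**Assumptions (none is in the documents).** Scale BCVA to variance 1 at each pre-dose visit. R is the reliability of one reading, hence also the Screening-Day 1 correlation. V is the variance of true change to Week 48. Where there is drift, G is the variance of true change from Screening to Day 1.

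**Residual variance of Week 48 BCVA, with G = 0** (analysing change from Day 1 with Day 1 as covariate gives the same treatment effect):
- Day 1 only: v1 = 1 + V - R²
- Day 1 and Screening: v2 = 1 + V - 2R²/(1 + R)

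**Price of the extra covariate.** With k covariates, chance imbalance multiplies the variance of the treatment contrast by about (N - 3)/(N - k - 3). Going from k = 2 to k = 3 at N = 24 costs (21/18)/(21/19) = 19/18 = 1.056. The net ratio is (v2/v1) × 1.056.

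| R | V | v1 | v2 | v2/v1 | Net ratio, 16:8 |
|---|---|---|---|---|---|
| 0.80 | 0.05 | 0.410 | 0.339 | 0.827 | 0.87 |
| 0.80 | 0.10 | 0.460 | 0.389 | 0.845 | 0.89 |
| 0.95 | 0.05 | 0.148 | 0.124 | 0.843 | 0.89 |
| 0.95 | 0.10 | 0.198 | 0.174 | 0.883 | 0.93 |
| 0.95 | 0.20 | 0.298 | 0.274 | 0.922 | 0.97 |
| 0.95 | 0.30 | 0.398 | 0.374 | 0.942 | 0.99 |
| 0.97 | 0.20 | 0.259 | 0.245 | 0.945 | 1.00 |
| 0.95, G = 0.05 | 0.10 | 0.198 | 0.183 | 0.926 | 0.98 |

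For the drift row, Day 1 variance is 1.05, Week 48 variance is 1.15, and the covariances are 0.95 (Screening-Day 1), 0.95 (Screening-Week 48) and 1.00 (Day 1-Week 48). Then v1 = 1.15 - 1/1.05 = 0.198, and v2 = 1.15 - (1.05 × 0.95² - 2 × 0.95² + 1)/(1.05 - 0.95²) = 0.183.

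Simulation of the same ANCOVA at 16:8 gives a net cut of about 6-12% for the first four rows and about 0-2% for the last four. The formula agrees to within about a point.

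**Power.** Take an effect of 1.06 residual SDs, borrowing SAP 7.1's figure. The noncentrality with Day 1 only is 1.06/√[(1/16 + 1/8) × 21/19] = 2.33 on 20 df, which gives 60.1%. With Screening added it is 1.06/√[(1/16 + 1/8) × (21/18) × v2/v1] on 19 df. That gives 62.9% to 65.7% for the first four rows and 60.0% to 61.0% for the last four.

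A wider set of correlations, with rb for Screening-Day 1 and r48 for each pre-dose value with Week 48, was simulated at 16:8:
- rb 0.8, r48 0.8: 60.2% to 68.4%
- rb 0.9, r48 0.8: 60.3% to 61.6%
- rb 0.95, r48 0.8: 60.6% to 60.8%
- rb 0.9, r48 0.6: 60.8% to 60.0%

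Type I error stayed near 5%. In the limit where Day 1 has no measurement error, v2 = v1, the variance rises by 5.6%, and power falls from 60.1% to 57.6%.

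**The case against.** The strongest case against is that nothing here is wrong. An ANCOVA on the Day 1 value plus the stratification factor is pre-specified, valid and consistent with the endpoint definition. That stands.

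It also stands that the gain depends on unstated quantities. The trial enrols children from age 2 with a progressive disease and permits cataract and glaucoma surgery, so true 48-week change could be well above 10% of BCVA variance. The favourable rows of the table cannot be taken as the expected case.

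Three stronger readings are tempting, and the documents do not support them:
- **That the model adjusts for Day 1 BCVA alone.** Age stratum is also in it. Day 1 is only the sole BCVA value used.
- **That precision is certainly lost.** At high reliability with larger true change, or with drift before Day 1, the gain is nil to about 2%.
- **That BCVA has no missing-data rule, so every subject without a Week 48 visit drops out.** SAP 10.1 does say "Missing data for the primary efficacy endpoint will be imputed through Week 48 using last observation carried forward", which names the primary endpoint only. But the surgery rule in the same section covers any affected assessment, carrying forward the last pre-surgery value. SAP 5 also maps an early-termination visit to the window that contains it or to the closest visit, and Protocol 8.2 and 10 call for end-of-study evaluations on discontinuation.

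What remains uncovered is BCVA missing at Week 48 without surgery or a nearby termination visit. Each such loss matters at 16:8. One placebo subject takes 1/16 + 1/8 = 0.1875 to 1/16 + 1/7 = 0.2054, a rise of about 10%. One ataluren subject takes it to 1/15 + 1/8 = 0.1917, about 2%. The documents do not say how many losses to expect, so the benefit of a repeated-measures model cannot be sized.

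**Conclusion.** The point holds as an efficiency suggestion. The BCVA test is sound as planned, but it leaves unused a pre-dose measurement that the schedule collects for every subject.

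At 16:8 the net variance of the treatment effect falls by about 6-12% if reliability is 0.80-0.95 and true 48-week change is 5-10% of BCVA variance. It falls by about 0-2% if reliability is at least 0.95 and true change is larger, or BCVA drifts before Day 1. The cost is about one power point in the poorest case simulated; only the extreme of an error-free Day 1 reading takes it to about two and a half. All power figures assume an effect of 1.06 residual SDs and describe the BCVA test on its own. Because BCVA is tested only after two earlier rejections, the benefit to a confirmatory claim is smaller.

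**What to change.** In SAP 7.7, before unmasking, name the BCVA model in full: change from Day 1 to Week 48, with treatment, age stratum, Day 1 BCVA and Screening (Visit 1) BCVA. Leave the endpoint and the SAP 5 definition of baseline unchanged. Take the Screening value from the same eye or eye summary and the same chart as the outcome, and say what happens if it is missing. The permission to explore other models is too loose to carry a gated test, so the covariate has to be written in.

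Optionally, specify a repeated-measures model on Week 24 and Week 48 BCVA with the treatment contrast at Week 48. With complete data it adds essentially nothing to that contrast. Its use is for subjects with Week 24 but no Week 48 value whom the surgery and early-termination rules do not reach.

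The cost is a change of SAP wording and one degree of freedom, with no new visit, procedure or data.
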